5. STUDY CALENDAR

	Screening (Day -42 to Day -1)	Cycle 1 ^m , 2 ^m		Cycle 3+ Day 1 ^m (-5 to +3d)	End of Treatment, 30 (±3) Day FU ^m	Long- term FU ^j
		Day 1 ^m (±3day for c2)	Day 8 ^m (±3 day)			
Informed Consent	X					
Medical/Surgical History, Demographics, Height Prior Histology (either report or clinician note as source)	X					
Biopsy of Metastatic Disease	X ^a					
Peripheral blood for germline and/or circulating tumor DNA	X ^b					
PE, Vitals ⁱ , Weight	X	X ^m	X ^m	X ^m	X ^m	
Performance Status	X	X	X	X	X	
Adverse Event, Toxicity Evaluations		X	X	X	X	
Medication Review	X	X	X	X	X	
Study Drug ^c		X	X	X		
Radiologic evaluations and measurements ^d	X (Must be ≤4 weeks from C1D1 or repeated) ^k			X ^e		
ECG	X (triplicate)	X ^g (C1D1 only)				
Serum Chemistry ^f , LDH	X	X	X (optional C2D8)	X	X	
PT (INR), APTT, Urinalysis ^h	X					
CBC with Differential	X	X	X (optional C2D8)	X	X	
PSA	X	X		X	X	

	Screening (Day -42 to Day -1)	Cycle 1 ^m , 2 ^m		Cycle 3+ Day 1 ^m (-5 to +3d)	End of Treatment, 30 (±3) Day FUm	Long- term FU ⁱ
		Day 1 ^m (±3day for c2)	Day 8 ^m (±3 day)			
Testosterone	X					
Circulating Correlatives		X ⁿ		C3D1 only ⁿ	X ⁿ	
Long-term follow- up for MDS/AML or new primary malignancy reporting						X

a. Biopsy must be done after patient has consented and registered to the study (unless pre-existing, CLIA certified lab, next-generation sequencing of metastatic mCRPC biopsy has been completed or mCRPC tissue available to submit for testing). Submitted tissue must be deemed adequate or fully reported prior to starting therapy.

b. Peripheral blood is sent for either germline comparison (if tissue also completed) or exploratory analysis of circulating tumor DNA and germline DNA if biopsy failed or is unsafe (and analysis available). If the biopsy is attempted and has insufficient tissue, new blood may not need to be redrawn as it was sent with biopsy.

c. For drug schedule see Section 1.2.

d. Radiographic evaluation will include radionuclide bone scan, CT or MRI of abdomen and pelvis, and CT, CXR or MRI of the chest as appropriate. All disease sites must be assessed using the same methodology as performed at baseline. At the discretion of the investigator, additional radiological evaluations may be performed at an unscheduled time point.

e. While receiving therapy, radiologic tests are performed every 8 weeks (±1 week) from C1D1. After the third scanning timepoint (~6 months), radiologic tests are performed every 12 weeks (±1 week) from C1D1.

f. Albumin, alkaline phosphatase, total bilirubin, BUN, calcium, creatinine, potassium, total protein, SGOT (AST), SGPT (ALT), sodium,

g. ECG is required \leq 7 days of C1D1 (C1D1 is adequate). Within the study, triplicate is not required unless the first ECG has a prolonged QTc per section 3.3.3.

h. Coagulation: activated partial thromboplastin time (APTT) will be performed at screening and if clinically indicated; international normalized ratio (INR) will be performed at screening and if clinically indicated. Patients taking warfarin may participate in this study; however, it is recommended that INR be monitored carefully at least once per week for the first month, then monthly if the INR is stable. Each coagulation test result will be recorded in CRF. Urinalysis will assess Hb/erythrocytes/blood, Protein/Albumin, and Glucose and should be performed at screening. After screening, urinalysis will only be required if clinically indicated.

i. Vitals include body temperature, blood pressure, pulse, respiratory rate, weight, height

- j. Follow all patients for MDS/AML and new primary malignancy assessment for up to 5 years after the patient completes the study per Section 7.7.1.
- k. To accommodate biopsy timing, the **screening** CT and bone scans to enroll allow for scans up to 6 weeks. If by the time therapy starts (to accommodate delays) prior scans will be >4 weeks from the planned start date of treatment, they must be repeated prior to C1D1 (≤ 4 weeks).
- m. Due to COVID 19 exposure risks AND for ease of patient participation, virtual visits are allowed for ALL visits except C1D1 (with windows of ± 3 days within C1 and C2, and $-5: +3$ for C3+). Regarding labs, local labs may be used with the same windows as visits (except for C2D8 where labs are optional). A single lab is preferred if possible, to minimize interlab variability. When the Morgan lab (see footnoteⁿ) is open, C1, C3D1 and EOT labs are preferred to be done at primary research sites to allow shipping of correlatives (but it is up to treating provider to balance tertiary care center COVID risks at that moment in time). Virtual visits should entail a video link with patients (via established, HIPAA compliant video visits). Phone visits are not preferred. For virtual visits, PE, weight and vitals will not be collected and are NOT deviations. See section 5.3.3 for drug shipping guidance.
- n. Due to COVID 19 exposure risks and guidance from the University of Michigan, the Morgan lab may have intermittent availability. The coordinating center (UMCCC) will update all sites with the status of the Morgan lab by email to keep sites aware on whether to collect specimens or not. This flexibility will avoid repeat amendments and IRB backlogs.

5.1 **Subject Enrollment and Initiation of Study Therapy**

Subjects will be identified through routine care of patients within the participating cancer centers. Each subject should meet all of the inclusion criteria and none of the exclusion criteria for this study.

5.2 **Procedures for Handling Subjects Incorrectly Enrolled or Initiated on Investigational Product**

Subjects who fail to meet the eligibility criteria should not, under any circumstances, be enrolled or receive study medication. Where a subject does not meet all the eligibility criteria and incorrectly started on treatment, the Investigator should inform the coordinating site and PI immediately, and a discussion should occur between regarding whether to continue or discontinue the patient from treatment. The coordinating site must ensure all decisions are appropriately documented.

5.3 **Treatments**

5.3.1 **Identity of investigational products**

The AstraZeneca Pharmaceutical Development R&D Supply Chain or a third party distributor/contractor will supply AZD6738 and olaparib.

Investigational products	Dosage form and strength(s)
AZD6738	20, or 80 tablet
Olaparib	100 or 150 mg tablet

5.3.2 Treatment plan

Agent	Dose	Route	Schedule	Cycle Length
AZD6738	160 mg	Oral	Once daily, Days 1-7	28 Days
Olaparib	300 mg	Oral	Twice daily, Days 1-28	

5.3.3 Agent administration + distribution

All treatment is rendered on an outpatient basis. Reported side effects and potential risks are described in Section 6.1/6.2 and dose modifications in Section 5.4. No other investigational or commercial agents or therapies other than those described below may be administered with the intent to treat the patient's malignancy (excluding LHRH agonists/antagonists). The research staff will provide detailed instruction and training for the handling of study drugs and administration at the beginning of the study to each patient. All dosages prescribed and dispensed to the patient and all dose changes during the study are recorded. The patient should contact the Investigator if he is unable to take the study drugs as prescribed.

Study drug may be shipped by each site's research pharmacy (if they are able to) via certified temperature-controlled container for overnight delivery, with tracking number and delivery signature required. Consultation with local research pharmacy is required and coordinating center must be notified that the local IRB and site is able to do this PRIOR to implementing site-> subject shipments. Sites are required to submit to coordinating center the subject diary and associated shipment processes for each cycle. The drug dispensation log must be updated as required noting direct shipment and copy of signature of receipt is encouraged to be obtained (if possible), placed in study records and be available for monitoring. Any non-receipt by subject/household must be reported to study staff locally so that shipment can be tracked and drug accounted for. Any missed dose of study medication is to be managed per protocol.

5.3.4 Labelling

Labels will be prepared in accordance with Good Manufacturing Practice (GMP) and local regulatory guidelines.

Each bottle of AZD6738 and olaparib will have an investigational product label permanently affixed to the outside stating that the material is for clinical trial/investigational use only and should be kept out of reach of children. The label will include the dosing instructions and a space for the enrollment code (E-code) to be completed at the time of dispensing.

The label will include the following information:

blank lines for quantity of tablets to be taken

enrollment code (E-code)

date of dispensing

Instructions stating that the AZD6738 tablets should be taken at approximately the same time each morning or evening

5.3.5 Storage

All study drugs should be kept in a secure place under appropriate storage conditions. The investigational product label on the bottle and the Investigator Brochure specifies the appropriate storage.

5.4 Management of Toxicity

5.4.1 Toxicities that require discontinuation from protocol therapy

Any toxicity observed during the course of the study should be managed in the first instance by interruption of the dose of study treatment and dose reductions if necessary. Repeat dose interruptions are allowed as required for a maximum of 28 days on each occasion. Treatment must be interrupted until the patient recovers completely or the toxicity reverts to NCI CTCAE grade 1 or 2 (depending on toxicity) or to the baseline CTCAE grade. If the required interruption is any longer than 28 days due to toxicity, the patient must be removed from the study. If at any point during study treatment, it becomes apparent that the tumor is not coming under control, patients are to be removed from study and treated as clinically indicated.

Protocol therapy should be discontinued if a patient experiences:

- Any CTCAE Grade 4 toxicity with the exception of:
 - CTCAE Grade 4 neutropenia of 5 days or fewer duration
 - CTCAE Grade 4 nausea, vomiting or diarrhea that resolves to Grade 3 in less than 72 hours in patients who have not received optimal anti-emetic or anti-diarrheal therapy
 - CTCAE Grade 4 laboratory abnormalities that can be readily corrected within 72 hours and do not result in hospitalization
- CTCAE Grade 3 or 4 thrombocytopenia with bleeding requiring hospitalization

5.4.2 Dose levels for olaparib and AZD6738

Both drugs have two levels allowed for dose reductions and may be dose reduced stepwise per instructions below. Once a dose is reduced, escalation is not permitted. All dose modification and interruptions (including any missed doses) and the reasons for the modifications/interruptions are to be recorded in the eCRF. Repeat dose interruptions are allowed as required, for a maximum of 4 weeks on each occasion.

AZD6738 has a unique aspect in that its hematologic toxicity (specifically neutropenia, leukopenia, thrombocytopenia, see section 5.4.5) is schedule rather than dose-dependent. For hematologic toxicities related to AZD6738 requiring a single dose reduction, the schedule is adjusted rather than the daily dose (see Table 1). Non-hematologic toxicities requiring dose reductions (as both drugs would be lowered by one level), daily dose is lowered rather than schedule. If both a hematologic (related to AZD6738 per 5.4.5) AND non-hematologic Grade 3+ toxicity requiring dose reduction occur concurrently, both drugs are dose reduced. Olaparib is reduced by one dose level, while if AZD6738 is on dose level 0 is reduced to dose level -2 at first reduction.

TABLE 1 Dose Modification Table for AZD6738

Dose Level	AZD6738
0	160 mg daily Days 1-7
-1 (Hematologic toxicity)	160 mg daily Days 1-4
-1 (Non-hematologic toxicity)	120 mg daily Days 1-7
-2	120 mg daily Days 1-4

TABLE 2 Dose Modification Table for Olaparib

Dose Level	Olaparib
0	300 mg BID Days 1-28
-1	250 mg BID Days 1-28
-2	200 mg BID Days 1-28

5.4.3 Hematologic Day 1 dosing requirement

Hematologic toxicity is anticipated to be the biggest challenge. To minimize this risk, there are clear Day 1 criteria (for any cycle) for both ANC and platelets. Both an ANC over 1000/ μ L and platelets over 75,000/ μ L are required to start each cycle. If either parameter is not met, treatment is delayed. If the patient has not recovered after 28 days, they are removed from protocol and please see section 5.13 for further hematologic workup.

TABLE 3 Day 1 minimum hematologic criteria

Treatment day blood counts and toxicity			
ANC		Platelets	Action
$\geq 1000/\mu\text{L}$	AND	$\geq 75,000/\mu\text{L}$	No dose modification or interruption
$< 1000/\mu\text{L}$	OR	$< 75,000/\mu\text{L}$	Delay by 1 week intervals until recovery

5.4.4 Management of anemia

Olaparib has shown the most suppression of red blood cells in prior studies, such that it is first reduced in lower risk anemia scenarios. At development of anemia, appropriate supportive treatment should be considered (per local guidelines) and alternate cause evaluation considered (e.g. iron, vitamin B12, folate, hypothyroidism). Investigator judgement to continue study treatment with or without supportive treatment (e.g. transfusion) or interrupt dose for a maximum of 4 weeks per guidance below. The use of erythropoietin is not allowed. For cases where patients develop prolonged hematologic toxicity causing >2-week interruption/delay in study treatment for CTCAE Grade 3 or worse anemia and/or blood transfusion dependence, refer to Section 5.4.14 for workup to consider.

Note, if at any time a dose reduction for a drug is required and the patient is already at dose level -2 for that drug, the patient must be removed from study.

Symptoms related to the Anemia (e.g. fatigue, shortness of breath) are designated by treating provider.

ASYMPTOMATIC Grade 2 Anemia (Hgb<10 and Hgb≥8 g/dL):

Asymptomatic Grade 2 anemia may be monitored and treatment continued without required delay or dose reduction. Delay, dose reduction and transfusions may be done at provider's discretion.

SYMPTOMATIC Grade 2 Anemia (Hgb<10 and Hgb≥8 g/dL) or ANY Grade 3 Anemia (Hgb<8 g/dL):

First episode:

1. Symptomatic Grade 2:

A treatment delay up to 28 days maximum (with or without blood transfusion) to allow resolution to asymptomatic Grade 2, Grade 1 or lower. Olaparib may be dose reduced or continued at current dose level.

2. Grade 3:

Treatment is delayed to allow resolution to asymptomatic Grade 2, Grade 1 or lower (up to 28 days maximum). Transfusions may be done at provider's discretion. Upon recovery, olaparib is reduced by one dose level (if possible).

Second episode:

3. Symptomatic Grade 2:

A treatment delay up to 28 days maximum (with or without transfusion) to allow resolution to asymptomatic Grade 2, Grade 1 or lower. Upon recovery, Olaparib is dose reduced by one level (if possible).

1. If olaparib was at full dose, AZD6738 dose/schedule is unchanged.
2. If olaparib was at dose level -1, AZD6738 is moved down one dose level. Either from dose level 0 to dose level -1 (hematologic toxicity, which is 160 mg daily Days 1-4) OR from dose level -1 (hematologic or non-hematologic) to dose level -2.

4. Grade 3:

Treatment is delayed to allow resolution to asymptomatic Grade 2, Grade 1 or lower (up to 28 days maximum). Transfusions may be done at provider's discretion. Upon recovery, olaparib is reduced by one dose level (if possible).

1. AZD6738 is moved down one dose level. Either from dose level 0 to dose level -1 (hematologic toxicity, which is 160 mg daily Days 1-4) OR from dose level -1 (hematologic or non-hematologic) to dose level -2.

Third episode:

5. Symptomatic Grade 2 or Grade 3:

A treatment delay up to 28 days maximum (with or without transfusion) to allow resolution to asymptomatic Grade 2, Grade 1 or lower. Upon recovery, Olaparib is dose reduced by one level (if possible).

1. AZD6738 is moved down one dose level to dose level -2 (if possible).

If no further reductions are possible because olaparib or AZD6738 are already at dose level -2, the patient should be removed from the study.

Fourth episode:

6. Symptomatic Grade 2: Patient is removed from study
7. Grade 3: Patient is removed from study

Any episode of Symptomatic Grade 2 or Grade 3 anemia in conjunction with Grade 2 or higher neutropenia, leukopenia or thrombocytopenia

Treatment is delayed to allow resolution of anemia to asymptomatic Grade 2, Grade 1 or lower and thrombocytopenia/leukopenia/neutropenia to Grade 2 or lower (up to 28 days maximum). Provider may do transfusions at their discretion. Upon resumption of therapy, olaparib is dose reduced by one level. AZD6738 is dose reduced by one dose level. Either from dose level 0 to dose level -1 (hematologic toxicity, which is 160 mg daily Days 1-4) OR from dose level -1 (hematologic or non-hematologic) to dose level -2.

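### Section 5.4.4: the third-anemia-episode step for AZD6738 names two different dose levels when the patient is still at level 0

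*Combined protocol and SAP*

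**What the plan says.** Section 5.4.4 (Management of anemia) works through successive episodes of symptomatic Grade 2 or Grade 3 anemia.

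- **First episode.** For symptomatic Grade 2, "Olaparib may be dose reduced or continued at current dose level". For Grade 3, "Upon recovery, olaparib is reduced by one dose level (if possible". Neither item changes AZD6738.
- **Second episode, symptomatic Grade 2.** Olaparib goes down one level. The AZD6738 action depends on where olaparib stood: "If olaparib was at full dose, AZD6738 dose/schedule is unchanged"; "If olaparib was at dose level -1, AZD6738 is moved down one dose level".
- **Second episode, Grade 3.** Both drugs go down one level.
- **Third episode, either grade.** Olaparib goes down one level, and "AZD6738 is moved down one dose level to dose level -2 (if possible". The text continues: "If no further reductions are possible because olaparib or AZD6738 are already at dose level -2, the patient should be removed from the study".

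The second-episode items and the paragraph on anemia combined with other cytopenias say what one level means for AZD6738. They treat a patient at level 0 separately from a patient at level -1, and the level 0 case reads "Either from dose level 0 to dose level -1 (hematologic toxicity, which is 160 mg daily Days 1-4". The third-episode item makes no such distinction.

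Table 1 in Section 5.4.2 lists level 0 as 160 mg on Days 1-7, level -1 for hematologic toxicity as "160 mg daily Days 1-4", and level -2 as 120 mg on Days 1-4.

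**The concern.** The third-episode item states both the size of the step (one level) and its destination (level -2). The two agree only for a patient who starts from level -1. If the earlier steps can leave AZD6738 at level 0, the sentence gives that patient two different regimens.

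What is at stake is consistent dosing across the four centers for a toxicity that the protocol expects. Section 5.4.3 anticipates hematologic toxicity as the main difficulty. Section 5.4.2 does not allow re-escalation after a reduction, so a site that takes the lower reading cannot go back up. Section 11.1 treats any dose above the specified regimen as a reportable overdose, which is hard to apply when the regimen can be read two ways. Dose modifications are also a reported result (Sections 10.1.2 and 10.3.3).

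**Working it through.** The plan has no statistical figure to reproduce here. The check follows the dose levels through the first two episodes and then applies the third-episode sentence.

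**Inputs.** Episode rules from Section 5.4.4; dose levels from Tables 1 and 2 in Section 5.4.2. Both drugs start at level 0, and no other toxicity or discretionary change is assumed.

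**AZD6738 per 28-day cycle** (daily dose × days):

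- Level 0: 160 × 7 = 1120 mg
- Level -1 (hematologic): 160 × 4 = 640 mg, and 640/1120 = 57% of the starting amount
- Level -2: 120 × 4 = 480 mg, and 480/1120 = 43% of the starting amount

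**Levels on reaching a third episode:**

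| First episode | Second episode | Olaparib | AZD6738 | Third-episode AZD6738 step |
|---|---|---|---|---|
| Symptomatic Grade 2, olaparib kept | Symptomatic Grade 2 | -1 | 0 | One level down gives -1; the named destination is -2: **conflict** |
| Symptomatic Grade 2, olaparib kept | Grade 3 | -1 | -1 | Both readings give -2: consistent |
| Olaparib reduced (optional for symptomatic Grade 2, required for Grade 3) | Either grade | -2 | -1 | Not applied: olaparib is already at -2, so the removal sentence governs |

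**The first row, step by step.**

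1. At the first episode the provider uses the stated option to continue olaparib at its current level. Levels: olaparib 0, AZD6738 0.
2. At the second episode olaparib was at full dose, so it drops to -1 and AZD6738 does not change. Levels: olaparib -1, AZD6738 0.
3. At the third episode neither drug is at -2, so the removal sentence does not apply and the dose step does. By the section's own definition, one level down from 0 is 160 mg on Days 1-4 (640 mg per cycle). The named destination is 120 mg on Days 1-4 (480 mg per cycle).
4. The gap is 640 − 480 = 160 mg per cycle, and 160/1120 = 14% of the starting amount.

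**Does other text settle it?** The qualifier about possibility does not. Level -2 can be reached from level 0, and the sentence that follows links impossibility to already being at -2. Section 5.4.2 describes reductions as stepwise. Its only stated direct move from level 0 to level -2 is for concurrent hematologic and non-hematologic Grade 3 or higher toxicity, which is not this situation. That context leans toward a single step, but the third-episode sentence names level -2 outright, so the literal conflict remains.

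**The case against.** The strongest reply is that a site has enough context to interpret the sentence. Section 5.4.2 calls for stepwise reduction, and the other anemia paragraphs define one level from 0 as level -1. This stands in part: the instruction is ambiguous rather than undefined. It does not remove the problem, because another site could fairly take the named destination as controlling.

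A second reply is that the route is narrow. It needs three qualifying episodes and an optional choice at the first. That is correct and limits the size of the point. The route still involves no deviation and no event outside the anemia rules.

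A reader might infer more than the documents support:

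- **That the conflict changes when patients are removed.** On this route olaparib goes from -1 to -2 at the third episode under either reading. A fourth episode then means removal whatever the AZD6738 level. Anemia with other cytopenias, and dose-reducing toxicity under Sections 5.4.5 and 5.4.6, also lead to removal because olaparib has no lower level. A difference could remain only where AZD6738 alone is reduced, for example at the investigator's discretion under Section 5.4.12.
- **That removal at the third episode after an early olaparib reduction is a contradiction.** It is not. The general note in Section 5.4.4 and the third-episode text state it consistently, and it follows from having two reduction levels. The fourth-episode rows can still be reached through the first two table rows.
- **That the conflict feeds the 25% toxicity-withdrawal rule in Section 10.3.4.** No such effect is shown, since removals under the rules above do not depend on which reading is taken.
- **That the number of branches measures how often this happens.** The documents give no episode probabilities, and other toxicities or discretionary reductions would change the starting levels.

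**Conclusion.** The third-episode AZD6738 step contradicts itself for a patient still at level 0. Section 5.4.4 permits exactly one route to that state: two symptomatic Grade 2 episodes with olaparib kept at full dose after the first. The two readings are 640 and 480 mg of AZD6738 per cycle, or 57% and 43% of the starting 1120 mg.

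This is a wording inconsistency in a dosing instruction. It matters for patient safety and for uniform treatment across sites. It does not bear on the sample size or the response-rate design. The conclusion assumes that both drugs start at level 0 and that no other toxicity or discretionary change intervenes. How many patients would follow this route cannot be derived from the documents. No view is taken on which regimen is right.

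**What to change.** Reconcile the third-episode sentence in Section 5.4.4 with the second-episode rule, Section 5.4.2 and Table 1. State the AZD6738 action separately for a patient at level 0 and a patient at level -1, using the layout already found in the second-episode and combined-cytopenia paragraphs. The sponsor decides which dose applies in each case.

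The cost is about one sentence of protocol text, with no new data, patients or procedures. The removal rules and the stopping rule need no change on account of this point.
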